13.0 AUDITING

As coordinating center of this trial, Washington University (via the Quality Assurance and Safety Monitoring Committee (QASMC)) will monitor each participating site to ensure that all protocol

requirements are being met; that applicable federal regulations are being followed; and that best practices for patient safety and data collection are being followed per protocol. Participating sites will be asked to send copies of all audit materials, including source documentation. The audit notification will be sent to the WUSM study team designee, who will obtain the audit materials from the participating institution.

Notification of an upcoming audit will be sent to the research team one month ahead of the audit. Once accrual numbers are confirmed, and approximately 30 days prior to the audit, a list of the cases selected for review (up to 10 for each site) will be sent to the research team. However, if during the audit the need arises to review cases not initially selected, the research team will be asked to provide the additional charts within two working days.

Items to be evaluated include:

- Subject screening and enrollment
- Reporting of adverse events
- Maintenance of HIPAA compliance
- Completeness of regulatory documentation
- Completeness of participant documentation
- Acquisition of informed consent
- IRB documentation
- Issues of protocol adherence

Additional details regarding the auditing policies and procedures can be found at https://siteman.wustl.edu/research/resources-for-researchers/quality-assurance-and-safety-monitoring/.

14.0 STATISTICAL CONSIDERATIONS

14.1 Statistical Hypotheses and Sample Size Determination

Chemotherapy alone has a pCR rate of 6-16%¹⁰. PCR is defined as a pathologic complete response (no tumor on gastrectomy specimen). We hypothesized that preoperative radiation followed by chemotherapy would result in a pCR rate of 20%, and with 36 patients, our confidence interval for this estimate will fall between 9% and 37%.

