	2. Average percentage difference in dose to nearby OARs (i.e.			
	duodenum, small bowel, large bowel) due to variation in OAR			
	position.			
	3. The percentage of patients in each TCGA molecular subtype			
	after radiation and chemotherapy.			
	4. The specific biomarkers			
	5. ctDNA levels			
Study Population:	Thirty-six adults of any gender who have a diagnosis of gastric cancer			
	and are receiving preoperative radiation followed by total neoadjuvant			
	chemotherapy will be enrolled.			
Phase:	Not applicable.			
Description of Sites /	This is a multicenter trial coordinated by and enrolling at Washington			
Facilities Enrolling:	University in St. Louis. The study will also open to enrollment at other			
	sites in the U.S.			
Description of Study	Patients undergoing preoperative radiation and chemotherapy for			
Intervention:	gastric cancer will undergo simulation for radiation treatment planning			
	on a conventional referenced CT scanner and ViewRay or Ethos			
	treatment machines. High resolution volumetric MR or CBCT images			
	will be acquired daily in the treatment position and OARs contoured by			
	the radiation oncologist. The new electronic density map will be used			
	to recalculate dose from the initial radiation plan (based on CT/MR			
	simulation) and treatment delivered to maximize coverage while not			
	exceeding dosimetric constraints.			
Study Duration:	36 months.			
Participant	12 months.			
Duration:				

SCHEMA

Eligible Patients Diagnosis of gastric adenocarcinoma

Treatment Plan

Adaptive 25 Gy / 5 fractions

followed by

Total neoadjuvant chemotherapy

followed by

Surgery

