1.0 SCHEDULE OF ACTIVITIES

Bereening pro		t tane place	, ,, ,,,,,,,,,,,,,,,,,,,,,,,,,,,,,,,,,,	100 44	. ,,,,,	egibtita						
	Screening	Baseline	Fx1	Fx2	Fx3	Fx4	Fx5	Chemo ⁴	Surgery ⁵	3-mo F/U ⁶	6-mo F/U ⁶	12-mo F/U ⁶
Informed consent	Х											
H&P, ECOG PS	Х									Х		
CBC w/diff ¹	Х											
CMP ¹	Х											
Pregnancy test ²	Х											
EUS	Х											
Institutional MRI	Х											
screening questionnaire	Λ											
Simulation		Х										
CT C/A/P		Х							X^8		Х	Х
PET/CT		\mathbf{X}^{11}										
Adaptive SCRT ³			Х	Х	Х	Х	Х					
SOC chemotherapy ¹⁰								Х		Х		
Gastrectomy									X ⁹			
Research blood for		Х						X^7	X ⁷		X ⁷	
ctDNA		Λ						Λ	Λ		Λ	
AE assessment	AEs will be tracked from baseline through 12 months after surgery/definitive											
	end of treatment. Refer to Section 8.0 for more details.											

Screening procedures must take place within 60 days of registration.

1. labs will be drawn as per SOC

2. women of childbearing potential only

3. patients will receive 5 fractions of radiotherapy delivered once daily; radiotherapy may take up to 10 business days (due to logistical delays)

4. SOC chemotherapy will begin 2-4 weeks after completion of radiotherapy

5. within 2-4 weeks after completion of SOC chemo

6. follow-up visits will take place at 3 months (+/-2 weeks), 6 months (+/-4 weeks), and 12 months (+/-4 weeks) post-surgery; patients who don't undergo surgery will have follow-up visits at 3 months (+/-2 weeks), 6 months (+/-4 weeks), and 12 months (+/-4 weeks) from the date of definitive end of treatment.

7. after completion of RT / prior to starting chemo, at completion of chemo / prior to surgery, and 6 months after surgery. See Section 9.2 for further details.

8. prior to surgery

9. tissue for research will be collected from patients who experience pCR

10. Any SOC total neoadjuvant chemotherapy regimen may be given at the discretion of and under the supervision of the treating medical oncologist

11. PET/CT is strongly encouraged at baseline but optional

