2.3 Study Design

2.3.1 Overall Design

The hypothesis of this study is that adaptive SCRT followed by multiagent chemotherapy will result in a pCR of at least 20%.

Thirty-six patients with gastric adenocarcinoma will be enrolled in this study. There will be a lead-in cohort of 5-10 patients (see Safety Cohort and Early Stopping Rules) to ensure there are no grade 5 toxicities related to adaptive SCRT (or SOC chemotherapy after adaptive SCRT). All patients will receive radiation delivered with MR or CBCT guidance followed by sequential chemotherapy. Gastrectomy will occur 2-4 weeks after the completion of chemotherapy. Pathologic response, plan dosimetry, and oncologic outcomes will be evaluated. FDG PET/CTs are strongly encouraged at baseline but optional. Patients will be followed on study for 12 months after surgery.

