6.3 Chemotherapy Guidelines

Chemotherapy will be given as per standard of care and should begin 2 to 4 weeks after completion of radiotherapy. Recommended total neoadjuvant chemotherapy regimens are:

- CAPOX (capecitabine/oxaliplatin)
- FOLFOX (oxaliplatin, leucovorin, and 5-FU)
- FLOT (docetaxel, oxaliplatin, leucovorin, and 5-FU)

However, the treating medical oncologist may prescribe other SOC total neoadjuvant chemotherapy regimen upon discussion with the WUSM PI. Additionally, if one regimen is not tolerated, subjects can move between regimens for a goal of 4 months of chemotherapy treatment total prior to surgery.

Patients who are unable to complete their total neoadjuvant therapy regimen may complete the chemotherapy postoperatively, at the discretion of the treating physician. Postoperative chemotherapy should start within 3 months of surgery. Patients who are medically inoperable will continue to receive chemotherapy until the entire regimen is complete.

A maximum (cumulative) delay of treatment of 4 weeks (or single delay of 3 weeks) is allowed per protocol due to factors/AEs listed in Section 7.0 (i.e., chemotherapy should be completed within a 5-month period). Cumulative delays in excess of 4 weeks, or single delays in excess of 3 weeks, will need to be discussed with the Principal Investigator in regard to proceeding to surgical resection. Such cases will need to be individualized depending on the clinical scenario. Please note that chemotherapy administration and AE assessment should be performed under the supervision of a medical oncologist. Dosing is to follow standard of care recommendations per institutional guidelines.

Interval imaging during chemotherapy, if obtained, is at the discretion of the treating physician.

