6.5 Patient Clinical Outcomes Data

Clinical outcomes data (including but not limited to patient demographics (age, date of birth, weight, sex, height), tumor staging, treatment delivered, pathologic response, local failure and distant failure) will be recorded in OnCore. Each patient will be deidentified with a unique patient identification number. Only those individuals at the patient's respective institution will have access to the patient's personal health identifiers (e.g. name).

Endpoint	In order to be evaluable for this endpoint, a patient must
Primary	
Rate of pCR	Have received at least one fraction of radiation therapy and undergone surgical resection
Secondary	
Proportion of patients able to complete a full course of total neoadjuvant chemotherapy	Have received at least one fraction of radiation therapy

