6.6 Definitions of Evaluability

Local control rate at 1 year post RT	Have received at least one fraction of
	radiation therapy and undergone at
	least one disease assessment
Rate of grade 3 or greater toxicity	Have received at least one fraction of
Rate of grade 5 of greater toxicity	
	radiation therapy
Overall survival at 1 year post RT	Have received at least one fraction of
	radiation therapy
Disease-free survival at 1 year post RT	Have received at least one fraction of
	radiation therapy and undergone at
	least one disease assessment
Exploratory	
Average percent difference in coverage of	Have received at least one fraction of
PTV by 95% isodose line	radiation therapy
Average percentage difference in dose to	Have received at least one fraction of
nearby OARs due to variation in OAR	radiation therapy
position	
Percentage of patients in each TCGA	Have completed radiation therapy and
molecular subtype after radiation and	neoadjuvant chemotherapy
chemotherapy	
Specific biomarkers	Have had specimens collected for
·	biomarkers
ctDNA	Have had specimens collected for
	biomarkers

Note that inevaluable patients will not be replaced.

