14.2 Analysis of the Primary Endpoint

The pCR rate will be described as percent with 95% confidence interval. Because only patients who undergo surgery are considered evaluable for the primary endpoint, the denominator used to describe the pCR rate will be the number evaluable. This will be described clearly when study results are reported.

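### The pCR precision in Section 14.1 (9% to 37%) is computed on all 36 enrolled patients, but only resected patients are analysed and none are replaced, so at a 20% rate it is the best case

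*Combined protocol and SAP*

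**What the plan says.** **Planned precision.** Section 14.1 assumes a pCR rate of 20% and states that "with 36 patients, our confidence interval for this estimate will fall between 9% and 37" percent. It gives no other reason for the number 36.

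**What 36 counts.** It is the enrolment figure. Section 2.3.1 says "Thirty-six patients with gastric adenocarcinoma will be enrolled in this study", and the Study Population row of the Protocol Summary agrees ("Thirty-six adults of any gender who have a diagnosis of gastric cancer").

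**Who is analysed.** The evaluability table of Section 6.6 sets this condition for the pCR endpoint: "Have received at least one fraction of radiation therapy and undergone surgical resection". Section 14.2 confirms that "only patients who undergo surgery are considered evaluable for the primary endpoint" and makes the number evaluable the denominator.

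**Replacement.** Section 6.6 ends: "Note that inevaluable patients will not be replaced".

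**Patients without surgery are foreseen.** Footnote 6 to the Schedule of Activities says "patients who don't undergo surgery will have follow-up visits at 3 months", counted from the definitive end of treatment. Sections 6.10 and 8.0 make the same provision for follow-up and adverse event tracking. Section 6.3 adds: "Patients who are medically inoperable will continue to receive chemotherapy until the entire regimen is complete".

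**The concern.** Two adjoining sections use different denominators for the same estimate. Section 14.1 computes the interval on everyone enrolled; Section 14.2 will compute it on those resected. Without replacement, the second number cannot exceed the first, and each patient who misses surgery lowers it. Section 14.1 gives no expected evaluable number and makes no allowance for such losses.

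This matters because the plan sets no hypothesis test, success threshold or futility rule for pCR, so expected precision is the whole case for the sample size. That precision should describe the patients who will be analysed. As written, someone approving or reading the plan is told of somewhat better precision than the trial is set up to deliver.

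**Working it through.** **Inputs**

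- Anticipated pCR rate: 20% (Section 14.1).
- Number enrolled: 36 (Protocol Summary, Section 2.3.1).
- Confidence level: 95% (Section 14.2), taken as two-sided because the sidedness is not stated.
- Denominator: patients with at least one radiation fraction and a resection (Sections 6.6 and 14.2), without replacement (Section 6.6).
- Resection rate: not in the documents. I assume about 90%, 80% and 70%. Then 0.9 × 36 = 32.4, 0.8 × 36 = 28.8 and 0.7 × 36 = 25.2, taken as 32, 29 and 25 patients.

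**Step 1: reproduce the printed figure.** With x = 0.20 × n responders, the exact (Clopper-Pearson) limits are:

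- lower = 2.5% quantile of Beta(x, n − x + 1)
- upper = 97.5% quantile of Beta(x + 1, n − x)

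For n = 36, x = 7.2. The lower limit, from Beta(7.2, 29.8), is 8.6%, and the upper limit, from Beta(8.2, 28.8), is 36.7%. These round to the printed 9% and 37%. Wilson with continuity correction gives 9.2–37.2%, which rounds the same way. Wald (6.9–33.1%), Wilson without correction (10.1–35.6%), Agresti-Coull (9.8–35.9%) and Jeffreys (9.5–35.1%) do not. The printed figure is therefore a correct calculation for 36 analysed patients.

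**Step 2: repeat it for fewer resected patients, holding the rate at 20%.** Widths and ratios use unrounded limits.

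| Resected | x = 0.2n | Exact 95% interval | Width (points) | Width relative to n = 36 |
|---|---|---|---|---|
| 36 (all) | 7.2 | 8.6–36.7% | 28.1 | 1.00 |
| 32 (about 90%) | 6.4 | 8.0–37.9% | 29.8 | 1.06 |
| 29 (about 80%) | 5.8 | 7.6–38.9% | 31.4 | 1.12 |
| 25 (about 70%) | 5.0 | 6.8–40.7% | 33.9 | 1.21 |

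**Step 3: check that the choice of method does not drive the result.** Wilson with continuity correction gives 9.2–37.2%, 8.7–38.4%, 8.3–39.5% and 7.6–41.3% for the same four numbers. The pattern is the same.

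**The case against.** **The denominator is disclosed.** Section 14.2 follows directly on 14.1, states the evaluable denominator and promises to describe it clearly in the report. Section 12 and Appendix E have evaluable counts reported during monitoring. A careful reader can see that 36 is a ceiling. This stands, and it rules out any suggestion of a concealed analysis rule. It does not correct the planning figure, which still uses a different denominator from the analysis.

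**The loss is small and of unknown size.** This also stands. At about 90% resection, 9–37% becomes 8–38%. The documents show that patients without surgery are expected to occur, but not how often.

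**Stronger readings that the documents do not support**

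- *The printed interval is correct only if all 36 are resected.* Section 14.1 does not name its method. With 35 resected, Wilson with continuity correction gives 9.1–37.5% (upper limit 37.46%), which still rounds to 9–37%; the exact method gives 8.4–36.9%, which does not. What can be said is that 36 resected is the best case.
- *No narrower interval is possible.* The comparison holds at a fixed 20% rate. A lower observed rate can give a narrower interval: 7/36 gives 8.2–36.0%, width 27.8 points.
- *The trial is underpowered or must enrol more.* The plan sets no test and no target width, so there is no power to lose and no precision requirement that is missed.
- *Sections 6.4 and 6.9 show that surgery will be omitted.* Section 6.4 calls for metastatic disease to be excluded, and 6.9 lists general reasons to stop treatment. Neither says that resection is then omitted. The direct evidence is in Schedule footnote 6 and Sections 6.3, 6.10 and 8.0.

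**Conclusion.** The point holds as a minor correction. The sole figure supporting n = 36 is calculated on enrolled patients, while the estimate it describes will use resected patients only. At a 20% pCR rate, 9–37% is therefore the most favourable interval that the design allows.

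Under assumed resection of about 90% to 70%, the exact interval widens by 1.8 to 5.8 points. The 20% rate comes from the plan; the resection rates are mine.

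A reader might infer that the trial's conclusion is at risk. It is not. The reported interval will use the true denominator, and no decision rule depends on it. The comparison with chemotherapy alone, for which Section 14.1 cites 6–16%, is not altered either: the lower limit already lies inside that range with 36 resected (8.6%) and stays inside it with 32, 29 or 25 (8.0%, 7.6%, 6.8%).

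**What to change.** In Section 14.1, state how many of the 36 are expected to be resected and evaluable, and give the interval for that number. For example:

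> Of the 36 patients enrolled, we expect about [x] to be resected and evaluable for pCR. At a pCR rate of 20%, the exact (Clopper-Pearson) 95% CI would be about 8–38% with 32 evaluable, 8–39% with 29 and 7–41% with 25; 9–37% is the best case, with all 36 resected.

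The sponsor supplies [x]. Clopper-Pearson is used here because it reproduces the printed figure. If another method was used, the limits should be recalculated with that one; naming the method is incidental to the point.

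The cost is a short edit to 14.1, a commitment to an expected number resected, and a slightly less favourable stated precision. Enrolment, endpoint, evaluability rule and analysis set do not change.

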14.2 Analysis of the Primary Endpoint

The pCR rate will be described as percent with 95% confidence interval. Because only patients who undergo surgery are considered evaluable for the primary endpoint, the denominator used to describe the pCR rate will be the number evaluable. This will be described clearly when study results are reported.

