APPENDIX D: Washington University Unanticipated Problem Reporting Cover Sheet	40
APPENDIX E: Study-Specific DSM Tables	41

PROTOCOL SUMMARY

Title:	Pre-operative Adaptive Short Course Radiation Therapy in Gastric Cancer					
Study Description:	Hypothesis : Adaptive radiation therapy followed by sequential multi- agent chemotherapy will result in a pathologic complete response (pCR) of at least 20%.					
	In this study, patients with gastric adenocarcinoma will receive hypofractionated adaptive radiation therapy followed by total neoadjuvant chemotherapy followed by surgery.					
Objectives:	Primary Objective: To quantify the pCR rate in gastric cancer patients treated with preoperative radiation followed by total neoadjuvant chemotherapy.					
	 Secondary Objectives: To quantify the proportion of patients able to complete a full course of total neoadjuvant chemotherapy To quantify the local control rate of gastric cancer patients treated with preoperative radiation followed by chemotherapy. To quantify the toxicity of gastric cancer patients treated with preoperative radiation followed by chemotherapy. To quantify the overall survival in gastric cancer patients treated with preoperative radiation followed by chemotherapy. To quantify the disease-free survival in gastric cancer patients treated with preoperative radiation followed by chemotherapy. 					
	 Exploratory Objectives: To quantify the deviation in dose to the tumor due to variation in stomach position. To quantify the deviation in dose to the nearby OARs due to variation in OAR position. To determine the distribution of TCGA molecular subtypes in gastric adenocarcinoma after radiation and chemotherapy. To identify differentially expressed post-treatment biomarkers in gastric tumors. To correlate circulating tumor DNA (ctDNA) levels with clinical outcomes. 					
Endpoints:	Primary Endpoint: The rate of pCR (both ypT and ypN) in gastric cancer patients treated with preoperative radiation followed by total neoadjuvant chemotherapy.					
	Secondary Endpoints: 1. Proportion of patients able to complete a full course of total neoadjuvant chemotherapy					

	2. The local control rate at 1 year post RT.			
	3. The rate of grade 3 or greater toxicity as defined by CTCAE v			
	5.0			
	4. The overall survival at 1 year post RT.			
	5. The disease-free survival at 1 year post RT.			
	Exploratory Endpoints:			
	1. Average percent difference in coverage of PTV by 95% isodose			
	line.			

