6.0 TREATMENT PLAN

Consenting and eligible patients will receive adaptive SCRT (25 Gy in 5 fractions), followed by standard of care total neoadjuvant chemotherapy followed by standard of care gastrectomy or esophagogastrectomy. The recommended SOC chemotherapy options are CAPOX, FOLFOX, or FLOT, but any SOC total neoadjuvant chemotherapy may be given at the discretion of the treating medical oncologist after consultation with the study chair. Patients who are not able to complete their full total neoadjuvant therapy regimen prior to surgery may complete chemotherapy postoperatively at the discretion of the treating physician.

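### The primary pCR rate drops treated patients who never reach resection, so it can only equal or exceed the rate among all treated patients, whom the objective and hypothesis describe

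*Combined protocol and SAP*

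**What the plan says.** Section 14.2 says that "only patients who undergo surgery are considered evaluable for the primary endpoint" and makes the number evaluable the denominator of the pCR rate, which is reported as a percentage with a 95% confidence interval. It promises that the report will make this denominator clear. The pCR row of the evaluability table (Sections 6.5–6.6) gives the matching rule: "Have received at least one fraction of radiation therapy and undergone surgical resection". Below the table is the line "Note that inevaluable patients will not be replaced".

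The objective and hypothesis are worded for a wider group. The primary objective is "To quantify the pCR rate in gastric cancer patients treated with preoperative radiation followed by total neoadjuvant chemotherapy". Section 2.3.1 states the hypothesis that the regimen "will result in a pCR of at least 20" percent. Section 14.1 gives the precision as "with 36 patients, our confidence interval for this estimate will fall between 9% and 37" percent, and 36 is the number to be enrolled.

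The plan expects some patients not to reach surgery. Section 6.3 says "Patients who are medically inoperable will continue to receive chemotherapy until the entire regimen is complete", Section 6.4 calls for metastatic disease to be excluded, and Section 6.9 lists progression, death and adverse events among the reasons to stop treatment. Section 1.0 (footnote 6) and Sections 6.10 and 8.0 set follow-up and adverse event tracking for patients who have no surgery.

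**The concern.** The primary estimate answers a narrower question than the objective asks. The objective asks how often the regimen produces a pCR in the patients who receive it. The planned rate is how often a pCR is found among those who got as far as resection.

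The patients who leave the denominator are not a random subset. Many will have progressed, died, had a serious adverse event, been found to have metastases or become inoperable, so several of these routes are treatment failures. Stopping chemotherapy early does not by itself remove a patient, because Section 6.0 provides that "Patients who are not able to complete their full total neoadjuvant therapy regimen prior to surgery may complete chemotherapy postoperatively".

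The trial has one arm and no formal test or go/no-go rule, so readers will compare the headline percentage directly with the hypothesised 20%. The choice of denominator can decide which side of 20% it falls on. Section 3.0 also presents a high pCR rate as a possible route to studies of non-operative management, and the relevant rate for that purpose is the one among patients who start treatment.

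**Working it through.** **Inputs from the documents.** Enrolled n = 36 (2.3.1). Assumed pCR rate 20% and stated interval 9–37% (14.1). Confidence level 95% (14.2), taken as two-sided. pCR means no tumour on the gastrectomy specimen (14.1). Inevaluable patients are not replaced (6.6).

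**Assumptions.** All 36 start radiation. No resection rate is given, so about 70–90% resected (25 to 32 of 36) is used to show the range.

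**Step 1: reproduce the stated interval.** The exact (Clopper–Pearson) limits for x of n are the 2.5% quantile of Beta(x, n − x + 1) and the 97.5% quantile of Beta(x + 1, n − x). With x = 0.20 × 36 = 7.2 and n = 36 they are 8.6% and 36.7%, which round to 9–37%. The precision statement therefore treats all 36 enrolled patients as evaluable.

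**Step 2: direction.** Let x be the number of pCRs, m the number resected and n the number treated, with m ≤ n. An unresected patient cannot be counted in x. The planned rate is x/m, the all-treated rate is x/n, and their ratio is n/m ≥ 1. The two are equal only if m = n or x = 0. This needs no assumption about the resection rate.

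**Step 3: size.** For each m, the table gives the smallest x with x/m ≥ 0.20, the same x as a share of 36, the all-treated rate implied by a reported 20% (20% × m/36), and the exact interval at 20% (x = 0.2m).

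| Resected m | Fewest pCRs for ≥20% | Reported rate | Same count of 36 | Reported 20% equals, of 36 | Exact 95% CI at 20% |
|---|---|---|---|---|---|
| 36 | 8 | 22.2% | 22.2% | 20.0% | 8.6–36.7% |
| 32 | 7 | 21.9% | 19.4% | 17.8% | 8.0–37.9% |
| 29 | 6 | 20.7% | 16.7% | 16.1% | 7.6–38.9% |
| 25 | 5 | 20.0% | 13.9% | 13.9% | 6.8–40.7% |

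One unresected patient is enough to cross the line: 7/35 = 20.0%, against 7/36 = 19.4%.

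**Step 4: one case in full.** With 29 resected and 6 pCRs, the planned rate is 6/29 = 20.7% (exact 95% CI 8.0–39.7%). Among all treated it is 6/36 = 16.7% (6.4–32.8%). The ratio is 36/29 = 1.24.

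No comparison is made with the 6–16% quoted for chemotherapy alone, because the documents do not state its denominator.

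**The case against.** The restriction is deliberate, specified in advance and disclosed. A pCR needs a specimen, Section 2.3.2 describes all patients as going on to resection, and a rate among resected patients is a legitimate conditional rate. A reader told the pCR count and the number treated could work out the other figure. This stands as far as it goes: nothing is hidden. But disclosing a denominator neither changes the headline estimate nor commits the report to an all-treated rate.

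The 20% is not a pass mark in Section 14, and the intervals overlap heavily: 7/35 gives 8.4–36.9% and 7/36 gives 8.2–36.0%. This is also true. The threshold counts show how the headline will read against the stated hypothesis, not the outcome of a test. The loss of precision is small, and the main issue is the shift in the estimate.

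The size rests on an assumed resection rate. That is correct; the direction does not.

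Read strictly, the objective covers patients who received radiation and then chemotherapy, which is narrower than everyone with one fraction. However, neither group is conditioned on surgery, and the current pCR row already starts from one fraction without requiring chemotherapy.

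One could instead reword the objective and hypothesis as conditional on resection and base the precision on the expected number resected. That would be consistent, but it would leave the rate for the regimen unreported.

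Two costs of the proposed change remain. A clinical complete responder who does not have surgery counts as non-pCR. And if the historical controls in Section 2.3.2 used resected patients only, the all-treated rate would not be like-for-like with them. Reporting both rates deals with each.

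**Conclusion.** The concern holds. The objective, hypothesis and precision statement describe one population, and the primary analysis uses a subset chosen after treatment. The reported pCR rate can never be below the all-treated rate when unresected patients count as non-pCR, and it is higher whenever there is at least one pCR and one unresected patient. If 70–90% of 36 treated patients are resected, which is an assumption, a reported 20% corresponds to about 14–18% of those treated, and the count needed to show 20% falls from 8 to between 5 and 7. Because this is the primary estimate of a single-arm trial, the denominator should be corrected before results are known.

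**What to change.** In Section 14.2 and the pCR row of the evaluability table:

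- Make the primary denominator all patients who received at least one fraction of radiation, the rule the plan already uses for chemotherapy completion, toxicity and overall survival.
- State that patients without resection are counted as non-pCR, as a conservative convention, and name the exact 95% interval.
- Report beside it the resection rate with reasons for non-resection, and the resected-only pCR rate with its exact 95% interval as a secondary estimate.
- For that secondary rate, say whether a patient who is explored but not resected is included; Section 14.2 refers to surgery and the table to resection.

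If all 36 are treated, the primary analysis then matches the n = 36 behind the interval in Section 14.1. The cost is wording only, since unresected patients are already followed and no further patients or data are needed. The headline rate will be less favourable, and a clinical complete responder without surgery will count against it; the secondary rate and the listed reasons make that visible.
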